Empower Opioid Misuse & Chronic Pain (RAP_EOM)

NCT04184362

5/1/2023

Contents:

- Study Protocol
- Statistical analysis plan

Study Protocol

This pilot study aims to examine the feasibility, acceptability, and preliminarily examine efficacy of transcutaneous electrical nerve stimulation (TENS) at the ulnar nerve, in reducing opioid craving and use and decreasing pain. Opioid prescribing for chronic pain has increased dramatically over the past several decades, with devastating public health consequences, including high rates of opioid misuse and overdose deaths. Safe nonpharmacological treatments are urgently needed. Preclinical studies have shown that peripheral nerve stimulation at the ulnar nerve (ulnar aspect of the palm) through acupuncture or electrical stimulation directly regulates the mesolimbic dopaminergic pathway and reduces addictive behaviors. In addition, neurostimulation at acupressure points may reduce some types of chronic pain. Empower (TheraNova, LLC) is a non-invasive, portable TENS device that provides electrical stimulation at the ulnar nerve, which may reduce cravings and improve pain. We propose a single-blind, randomized controlled trial to examine the feasibility and to preliminarily examine efficacy of Empower in reducing opioid craving and opioid use in Veterans with chronic non-cancer pain (NCP). Aims are to examine the feasibility and acceptability of Empower and preliminarily examine its efficacy in reducing cravings, decreasing opioid use, and reducing pain when used at the ulnar nerve. Up to thirty veterans with chronic NCP and opioid misuse will be recruited. On Days 1- 7, participants will undergo baseline monitoring, and on Days 8-21, participants will undergo daily neurostimulation at ulnar nerve (n=15) or a control acupoint on the dorsal bicep (n=15). Study procedures will occur at home over 3 weeks, through secure two-way video or phone conference, with outcome assessments occurring at Days 0, 7, and 21. Pain scores, craving, and opioid use will be measured daily Days 0-21. Our goal is to provide an intervention that, alone or in conjunction with current treatments, reduces craving and reduces reliance on opioids in high-risk chronic pain patients.

PROCEDURE

In this proof-of-concept study, we will use a single-blind, randomized controlled design to assess feasibility, acceptability, and preliminarily examine efficacy of Empower in reducing opioid craving, opioid use, and pain levels in 30 Veterans with chronic NCP and opioid misuse. After screening, participants will undergo a 7-day no-treatment Baseline Monitoring Period, during which they will complete daily self-report measures of craving and pain. Participants will then take home the Empower device over a 14-day intervention period, during which they will receive neurostimulation at the ulnar nerve (n=15) or neurostimulation at a different anatomical location (Dorsal bicep) (n=15), twice daily, for 15 min on each side of the body (30 min per treatment; 60 min total per day). Study procedures will occur over 3 weeks, with in-clinic assessments occurring at or around Days 0, 7, 14, and 21. Primary outcomes include: opioid craving, prescribed and nonprescribed opioid use, and pain scores; and qualitative and quantitative measures of usability and acceptability at treatment end. Exploratory outcomes include self-reported depression levels, activity scores, and health-related quality of life, and the association between pain scores and craving levels over time.

The total duration of participant participation will be three weeks. At screening, self-report and interviewer data will be reviewed to determine participant eligibility. Medical conditions, psychiatric history, and medication list will be collected through review of participants' VA medical records. Participants will complete the MINI Neuropsychiatric Inventory. Urine toxicology panels may be completed through either VA lab urine drug screen or urine drug screen home test kits for participants at Days 0, 7, and 21. During pandemic times, if a participant is already scheduled for an essential visit to the hospital and lab, then they may optionally take the test at the lab. However, due to pandemic restrictions, we will also offer at home test kits for participants who will not be attending the VA site for an essential

visit. To encourage self-monitoring during treatment sessions, participants may optionally self-monitor heart rate variability, through their own at-home heart rate monitors or through provision of commercialized heart rate monitoring apps. Interested participants will be informed that they may optionally monitor heart rate before, during, or after treatment sessions at Days 0, 7, 14, and 21, from home. Readings will be collected via encrypted message, de-identified and stored in the password protected database.

A urine pregnancy test in women ages 18-50 who do not confirm a reliable method of birth control at screening will also be completed at screening (Day 0), either in the VA lab or at home. The results of at home urine pregnancy test can be shared securely via encrypted email through a photo image of the home test. We will obtain informed verbal consent to communicate with each participant's medical provider to confirm eligibility after verbal consent. Participants who meet all inclusion criteria and none of the exclusion criteria will be enrolled in the study.

The first week (Days 0-7) will be the Baseline Monitoring Phase, in which baseline measures of craving, and pain are completed daily (see below). On Day 7, participants will be randomized to use the Empower device at the ulnar nerve (Treatment Group, n=15) or at the bicep (Sham Group, n=15). The subsequent two weeks will be the Treatment Phase, followed by the Post-Treatment Completion visit at the end of the two- week Treatment Phase. Throughout the study, the participant will complete daily surveys on the Empower app on the provided smartphone and weekly Qualtrics-based questionnaires. The participant will be asked to complete surveys as close as possible to awakening. During the Treatment Phase only, the participant will self-administer a 30-minute treatment two times daily. The participant will be asked to administer treatments approximately 12 hours apart, if possible. The smartphone will have daily notifications to remind the participant to complete surveys and treatments.

The study will include three clinic visits:

- 1) Enrollment and start of Baseline Phase (Day 0),
- 2) Completion of the Baseline Phase and start of the Treatment Phase (Day 7, \pm 5 days to account for scheduling/ weekends), and
- 3) Study Completion (14 \pm 5 days after Visit 2).

At Baseline (Day 0), the participant will be given the smartphone with Empower app and trained on smartphone and app use. The participant will then be sent home with the smartphone and instructions for use. They will record craving levels and pain levels daily on the Empower app. On Day 7, the study team will use a secure two-way video or telephone conference app to randomize participants into one of two groups (treatment condition (palm) or control condition (dorsal bicep) in a 1:1 ratio according to a computer-generated code provided by the study biostatistician using randomization software. Participants will be randomized in blocks of random size ranging between 4 and 6 to ensure equal numbers in each group and to maintain relative balance between groups as the study progresses. After enrolling a participant into the study, all study materials and devices will be securely delivered to the participant. When the receipt of the materials is confirmed with the participant, study staff will coordinate a tutorial on how to use the device using secure two-way video or telephone conferencing. Once participants demonstrate an understanding for how to use the Empower Neuromodulation System at their designated site, they will then undergo their first self-administered electrostimulation session under study staff supervision.

Starting on Day 8, all participants will self-administer neurostimulation via Empower upon awakening (immediately following completion of the Empower App self-reports) and again approximately 12 hours later. Treatment Condition: Participants will complete a 15-min electrical stimulation application via

Empower on one palm (ulnar nerve acupoint) followed by an additional 15-min stimulation on the opposite palm (30 min per session, 60 min per day). Control Condition: Empower will deliver equal electrical current to the dorsal aspect of the bicep for equal time duration as the Treatment condition.

Surveys administered through Qualtrics will be conducted through secure two-way conferencing or encrypted e-mailed to participants through Qualtrics. The e-mails will contain no health information and will only contain the link to the survey in which a participant will submit their responses, and what week of the study they are in. The survey links will be anonymized as to not retrieve any IP address information from participants and will also be de-identified and participants will be entering their subject ID numbers rather than any identifiable information. The e-mail will be sent from a no-reply Qualtrics server. At the final assessment day, after the participant has completed their last self-administered treatment session, the clinical research staff will determine if any adverse effects (AEs), serious adverse effects, SAEs, or UADEs or other side effects have occurred during the study. The participant will also complete the weekly measures along with the usability survey on Qualtrics.

Statistical Analysis Plan

Prior to analysis, all data will be examined for anomalous and missing values and described in detail. To address missing data, we will perform a sensitivity analysis using a “copy reference” approach, under which missing-at-random data in either condition is imputed. The description of the data is a key aspect of this work as it informs future studies. Aim 1: Measures of feasibility, including proportion of those eligible among those screened, proportion enrolled among those eligible, enrollment rate, study retention, adherence to the baseline monitoring period, adherence to the treatment and control conditions, study completion rate, and potential adverse effects will be calculated. We will also passively collect data about participant usage patterns (compliance and electrical current). Qualitative data examining acceptability will be analyzed using an iterative, inductive process. We will meet approximately biweekly to conduct multiple reviews to identify prominent themes and develop coding templates based on new data emerging from interviews and using grounded theory methodologies. Mean quantitative acceptability data will be calculated, with a target of SUS ≥ 70 and CSQ ≥ 24 . Lower scores would lead to revision of product design or other features to improve acceptability.

Aims 2-3 and Exploratory Aims: Outcome measures will be examined with a series of parallel statistical models, estimated via maximum likelihood, using planned contrasts between the Empower active ulnar nerve treatment condition, the control condition, and the baseline monitoring period. Analyses of in-clinic assessments will compare outcome measures at Days 0, 7, 14, and 21. Given the limited number of assessment points, the most parsimonious model will be a general linear model for each outcome measure. For the daily measures, we will use multilevel modeling to compare changes in variables over days between the treatment and control condition/baseline monitoring period. Analyses will be performed with SPSS.

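### Is opioid use, a primary outcome, left without a daily measure and without an analysis model?

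*Combined protocol and SAP*

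**What the plan says.** The opening paragraph of the Study Protocol gives one schedule for three outcomes: "Pain scores, craving, and opioid use will be measured daily Days 0-21". The PROCEDURE section sets their status: "Primary outcomes include: opioid craving, prescribed and nonprescribed opioid use, and pain scores", together with usability and acceptability at the end of treatment.

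The PROCEDURE section describes the daily baseline record three times. Participants have a monitoring week "during which they will complete daily self-report measures of craving and pain". The paragraph on the first week repeats craving and pain. On the smartphone handed over at Day 0, "They will record craving levels and pain levels daily on the Empower app". None of the three mentions opioid use. The same section also says: "Throughout the study, the participant will complete daily surveys on the Empower app on the provided smartphone and weekly Qualtrics-based questionnaires". It does not list the items of either instrument.

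The only drug test described is urine toxicology: "Urine toxicology panels may be completed through either VA lab urine drug screen or urine drug screen home test kits", at Days 0, 7 and 21.

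Under Aims 2-3 and Exploratory Aims, the SAP provides a general linear model for in-clinic assessments and multilevel modelling for daily measures, with the baseline monitoring period as one comparator. It lists no outcome by name under either model.

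**The concern.** A primary outcome needs a variable behind it. For opioid use the documents do not say whether that is a dose, a yes/no answer or a count of days, what period the question covers, or how prescribed use is separated from nonprescribed use. Craving and pain also lack named scales, but both are at least placed in the daily app record.

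Two things would be at stake. First, if the app did not ask about opioids during the baseline week, the multilevel model would have no baseline series for this outcome, and the between-arm comparison would lose the precision that baseline adjustment brings. Second, with an app item, a weekly questionnaire and a urine panel all conceivable, the analysed version could be chosen after the data were seen.

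**Working it through.** The plan gives no sample size, power or effect figure on this point, so there is nothing of its own to reproduce. The check sets the passages side by side, then asks when the feared loss could arise.

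**1. Do the passages conflict?** The opening paragraph explicitly names opioid use as daily on Days 0-21. The three baseline descriptions are shorter and contain no word such as *only*. A shorter list that is not said to be complete does not cancel an explicit statement, and the daily app survey is described for the whole study without an item list. This is incomplete description, not contradiction.

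**2. Which model applies?** The SAP sorts outcomes by schedule, not by name. Opioid use is stated to be daily, and daily measures go to multilevel modelling. Craving and pain reach their model by the same inference, so opioid use is no worse placed. *Multilevel* does not fix the outcome distribution either: a yes/no item would take a logistic form and a continuous one a linear form.

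**3. How much data does the stated schedule imply?**
- Daily records: Days 0 to 21 is 22 per participant; 22 × 30 = 660 at most.
- Baseline part: 8 × 30 = 240 (Days 0-7, PROCEDURE) or 7 × 30 = 210 (Days 1-7, opening paragraph).
- Urine: 3 × 30 = 90 readings at most.

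**4. When would precision be lost?** There are three possibilities for the app.
- *Opioid items throughout the study.* Nothing is lost.
- *No opioid items at all.* The daily treatment-phase mean is missing as well, so a comparison with and without daily baseline does not arise. This would also contradict the opening paragraph.
- *Opioid items in treatment but not at baseline.* Only here does the loss of precision apply.

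For the third case, take 15 per arm, total variance 1, between-person share *s*, independent days, and treatment Days 8-21. Then SE = √[(2/15)·V].
- No baseline: V = s + (1 − s)/14.
- Mean of *k* baseline days as covariate: V = s + (1 − s)/14 − s²/[s + (1 − s)/k].

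With s = 0.3:
- No baseline: V = 0.3 + 0.7/14 = 0.350; SE = 0.216.
- Days 0 and 7 only (k = 2): V = 0.350 − 0.09/0.65 = 0.212; SE = 0.168.
- Daily Days 0-7 (k = 8): V = 0.350 − 0.09/0.3875 = 0.118; SE = 0.125.

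Relative to daily baseline, the ratios are 0.168/0.125 = 1.34 and 0.216/0.125 = 1.72 (from unrounded SEs). Over s from 0.3 to 0.7 and day-to-day autocorrelation of 0 or 0.5, they run from 1.05 to 1.59 (two baseline days) and from 1.33 to 3.56 (none).

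The variance shares and autocorrelations are assumptions; the documents give none. The scenario is an assumption too. The PROCEDURE section has one app survey running throughout, and nothing suggests that opioid items begin only with treatment. The ratios illustrate what a baseline series is worth; they do not measure a defect in this plan.

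**5. Does the urine panel undercut the daily schedule?** No. It is a separate assessment on three days, not presented as the measure of opioid use, and it can be analysed only on the days it is collected. The permissive wording can refer to the route (hospital laboratory or home kit), since the text that follows explains when each is offered.

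**The case for a change.** The strongest reply is that inference is a weak basis for a primary outcome. Three separate descriptions leave opioid use out of the daily record, including the one closest to an account of what participants enter on the app. The variable's type also decides the form of the model: a general linear model would not suit a positive or negative urine result. A pilot meant to inform later studies should say what it measured, and doing so would cost a sentence.

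Part of this stands. Source, unit, recall period and the split between prescribed and nonprescribed use are not stated, and naming them would make the document clearer. The freedom to choose among sources afterwards is real but modest. An analysis resting on three urine readings would visibly depart from the declared daily schedule. Efficacy is examined only preliminarily here, and the SAP treats description of the data as a key part of the work. The omission does not show that baseline opioid data are missing or that the randomised comparison is compromised.

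A neighbouring mismatch should be kept apart. The PROCEDURE section's opening and the SAP include an in-clinic assessment at Day 14, while the Study Protocol's opening paragraph gives Days 0, 7 and 21 and the visit list has three visits. That is a matter of aligning wording. Weekly questionnaires run throughout, and the mismatch does not bear on how opioid use is defined.

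**Conclusion.** The omission is real, but it is a gap in description that an analyst fills sensibly. Following the opening paragraph and the SAP as written gives a daily opioid-use measure, up to 22 records per participant, analysed in the multilevel model with a form suited to the item actually asked. The demonstrated loss of precision is nil. The ratios of roughly 1.05 to 3.56 need a pattern of data collection that the documents do not describe, together with variance assumptions from outside them. The between-arm comparison rests on randomisation and stands in every case.

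This conclusion assumes that the daily schedule in the opening paragraph means what it says and that the app survey carries opioid items accordingly. The documents do not list those items, so this is a reading of the text and not a confirmed fact. No change to the plan is called for.

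### The ±5-day window on Visit 2 does not secure the stated 7-day baseline: a visit within the window can leave 2 post-enrolment ratings, and no minimum is set

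*Combined protocol and SAP*

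**What the plan says.** All statements are in the combined protocol and SAP.

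- **Phase lengths (Procedure).** "participants will undergo a 7-day no-treatment Baseline Monitoring Period", and "Participants will then take home the Empower device over a 14-day intervention period". Total time on study: "The total duration of participant participation will be three weeks".
- **Fixed calendar.** The opening summary puts baseline on Days 1 to 7, and "on Days 8-21, participants will undergo daily neurostimulation at ulnar nerve" or at the control site. It has craving, pain and opioid use rated daily from Day 0 to Day 21. The Procedure section says "The first week (Days 0-7) will be the Baseline Monitoring Phase", places randomization on Day 7, and starts stimulation on Day 8 for everyone.
- **Visit-based calendar (Procedure, list of clinic visits).** Visit 2 is "Completion of the Baseline Phase and start of the Treatment Phase (Day 7", with a tolerance of plus or minus "5 days to account for scheduling/ weekends". Visit 3 is 14 ± 5 days after Visit 2.
- **Daily ratings (Procedure).** "Throughout the study, the participant will complete daily surveys on the Empower app", preferably close to awakening.
- **Analysis (Statistical Analysis Plan, Aims 2-3).** Daily measures go into a multilevel model that compares treatment with the control condition and the baseline period. Aim 1 reports adherence to baseline monitoring as a feasibility measure.

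No minimum number of baseline days or ratings is given.

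**The concern.** The window is nearly as wide as the phase that it closes. Visit 2 by definition ends baseline and starts treatment, so moving it early shortens the untreated period day for day. The fixed-day statements and the visit-based statements cannot all hold for a participant whose Visit 2 is not on Day 7. If Visit 2 is on Day 2, either treatment starts then and the seven untreated days are lost, or stimulation waits until Day 8 and Visit 2 does not start treatment.

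Craving, pain and opioid use are primary outcomes rated daily, and the baseline period is one of the comparators named in the SAP. A participant with very few baseline ratings contributes a noisy reference to that contrast. Baseline adherence is also harder to interpret when its denominator can run from 2 to 12 days. In a pilot of up to 30 people, whose data description is meant to inform later studies, phase length should not be left to scheduling.

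**Working it through.** **Inputs from the documents:** Visit 2 on Day 7 ± 5; a 7-day baseline; a 14-day intervention; Visit 3 at 14 ± 5 days after Visit 2; a rating each morning. **Assumptions:** the first session takes place on the day of Visit 2, after that morning's rating (the documents give no day for the supervised first session); day-to-day correlation of 0, 0.3 or 0.5 within a person.

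**Step 1. Day counts.** With Visit 2 on day v, post-enrolment baseline ratings fall on Days 1 to v, so there are v of them. Treatment days are v+1 to v+14.

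- Planned schedule, v = 7: 7 baseline ratings and treatment on Days 8 to 21. This reproduces the stated 7 and 14 days.
- Earliest visit, v = 7 − 5 = 2: 2 baseline ratings (3 with Day 0), treatment on Days 3 to 16.
- v = 5: 5 baseline ratings.
- Latest visit, v = 7 + 5 = 12: 12 baseline ratings, treatment on Days 13 to 26.

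**Step 2. Cost in precision for one participant.** Take k baseline and m treatment ratings, and express variance in units of the daily within-person variance. With independent daily errors, the variance of (treatment mean − baseline mean) is 1/k + 1/m:

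- k = 7, m = 14: 1/7 + 1/14 = 0.214
- k = 2, m = 14: 1/2 + 1/14 = 0.571; ratio 0.571/0.214 = 2.67
- k = 5, m = 14: 1/5 + 1/14 = 0.271; ratio 1.27

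Counting Day 0 in both schedules compares 3 ratings with 8: (1/3 + 1/14)/(1/8 + 1/14) = 0.405/0.196 = 2.06.

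For correlated days the variance is w′Rw. Here w is −1/k on baseline days and +1/m on treatment days, and R has entries ρ^|i−j| (first-order autoregression, with the two phases adjacent).

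| Ratio to planned schedule | ρ = 0 | ρ = 0.3 | ρ = 0.5 |
|---|---|---|---|
| 2 vs 7 baseline ratings | 2.67 | 2.08 (0.737/0.354) | 1.67 (0.837/0.501) |
| 3 vs 8, with Day 0 | 2.06 | 1.78 | 1.53 |
| 5 vs 7 | 1.27 | 1.22 | 1.16 |

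**Step 3. Visit 3.** Its window allows 14 − 5 = 9 days after Visit 2, even when Visit 2 is exactly on Day 7. A study-completion visit can therefore close a 14-day treatment phase after 9 days.

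**Step 4. Scale across the trial.** If one of 30 participants had the 2-day baseline, the average within-person variance would be (29 + 2.67)/30 = 1.056 times the planned value at ρ = 0, and (29 + 1.67)/30 = 1.022 times at ρ = 0.5. That is a rise of about 2% to 6%.

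**The case against.** The best defence is that a Day 2 start is the corner of the window least consistent with the rest of the protocol. Randomization is stated for Day 7, stimulation for Day 8, and nobody can be told palm or bicep before randomization. The window exists for scheduling and weekends, so most visits may fall close to Day 7. The variance ratios describe one participant at the extreme, and they leave out between-person variation in response, which would dilute them. These points limit the size of the problem but do not remove it: the fixed days conflict with the window, and nothing in the text says which prevails.

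Three stronger readings are tempting, and the documents do not support them.

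- **Lost treatment ratings.** After a Day 12 Visit 2, a stop at Day 21 would leave 21 − 12 = 9 of 14 treatment days rated. This holds only if the Day 0 to 21 span in the summary and the three-week total override the Procedure section. That section runs surveys for the whole study and times Visit 3 from Visit 2, so the loss is not established. A late visit does not raise the variance either: with 12 baseline and 9 rated treatment days the ratio is 0.91 to 0.94.
- **Misclassified scores.** Coding by nominal day would misplace some scores, but no such coding is proposed. Visit 2 is the stated boundary, and coding by actual date misplaces none. What is missing from the SAP is a sentence of detail.
- **Bias between arms.** Both arms share the window, and Visit 2 is timed before allocation is made. An unadjusted end-of-treatment comparison between arms does not depend on baseline length.

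**Conclusion.** The concern holds for the baseline. As written, a Visit 2 within its window can leave 2 post-enrolment baseline ratings (3 with Day 0) where seven untreated days are stated, and the same window contradicts the fixed days for randomization and stimulation. For that participant the variance of the within-person contrast rises about 1.5- to 2.7-fold; with a 5-day baseline (Day 0 not counted) it rises about 1.2- to 1.3-fold. The day counts come from the documents. The variance range rests on assumed correlations of 0 to 0.5 and equal daily variance. The documents give no spread of visit dates, so the number of participants affected is unknown. The consequence is lost precision and an unclear baseline, with neither arm favoured. It should be corrected because the remedy is cheap, but it does not threaten the trial's validity.

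**What to change.** **Main change.** Set the Visit 2 window to 0 to +5 days (Days 7 to 12), and tie randomization and the supervised first session to that visit in place of fixed Days 7 and 8. Every participant then has at least 7 scheduled baseline days, and there is still room for weekends and scheduling.

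**Accompanying clarifications.**

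- In the SAP, assign each daily score to a phase by the actual date of the first session: ratings before it are baseline, and the 14 days that follow it are treatment. Report each participant's phase lengths.
- Continue daily ratings through treatment day 14 even when that falls after Day 21, and amend the Day 0 to 21 span and the three-week total to match.
- Set the Visit 3 window to 0 to +5 days from day 14 after Visit 2, so that it cannot cut treatment to 9 days.

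**Cost.** Staff lose the option of an early Visit 2 or Visit 3. A participant with a Day 12 Visit 2 would rate up to Day 12 + 14 = 26, which is 5 days beyond Day 21. The latest possible Visit 3 stays at Day 12 + 19 = 31, as now. The rest is wording and one SAP definition. If early visits must be kept, a stated minimum number of baseline ratings before randomization would be a weaker substitute.

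### All efficacy models are set to maximum likelihood in at most 30 people with no small-sample method; read literally, a two-arm standard error is 3.4% too small, and for the daily models this depends on random effects the plan does not state (minor).

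*Combined protocol and SAP*

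**What the plan says.** The paragraph of the Statistical Analysis Plan on Aims 2-3 and the exploratory aims opens with the estimator for every efficacy model: "Outcome measures will be examined with a series of parallel statistical models, estimated via maximum likelihood". It then names two kinds of model.

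- In-clinic assessments: "Given the limited number of assessment points, the most parsimonious model will be a general linear model for each outcome measure".
- Daily measures: "For the daily measures, we will use multilevel modeling to compare changes in variables over days". The comparison is between the treatment condition and the control condition or baseline period.

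The software is SPSS, with no procedure or options given. The plan does not mention REML, a degrees-of-freedom method, a t, F or normal reference distribution, the random effects of the daily model, or an alpha for efficacy.

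On size, the opening summary of the Study Protocol says "Up to thirty veterans with chronic NCP and opioid misuse will be recruited", and the Procedure section gives 15 per arm. On which outcomes reach the daily model, the summary says "Pain scores, craving, and opioid use will be measured daily Days 0-21", and the Procedure section describes a baseline phase "in which baseline measures of craving, and pain are completed daily". The Procedure section lists craving, opioid use and pain among the primary outcomes, so the daily model carries primary outcomes. On purpose, the SAP says "The description of the data is a key aspect of this work as it informs future studies".

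**The concern.** ML variance estimates make no allowance for the mean parameters estimated from the same data. In a large trial this does not matter. With 15 people per arm it makes standard errors and reported variances systematically too small, and a normal reference distribution, if used, would add to the effect. The plan names ML outright and offers no correction.

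The stake is the width of the intervals and the accuracy of the variances that the pilot reports. No efficacy decision hangs on it, because the plan sets no alpha and no efficacy decision rule. It still deserves a line, because the SAP treats description of the data as a main product of the study and the correction is almost free.

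**Working it through.** The plan has no alpha, power or sample-size figure, so there is nothing of its own to reproduce.

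**Inputs.** From the documents: n = 30 at most, 15 per arm, about 7 baseline and 14 treatment days per person. Assumed: two-sided alpha 0.05, analysed numbers of 24 or 20, and the standard deviations (SDs) in steps 3 and 4.

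**1. Person-level contrast.** ML divides the residual sum of squares by n; the unbiased estimate divides by n − p, where p is the number of mean parameters. So

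SE(ML) / SE(unbiased) = √((n − p)/n).

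For n = 30, p = 2: √(28/30) = 0.966, which is 3.4% too small. Conversely √(30/28) = 1.035, so the unbiased standard error is 3.5% larger.

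The actual size of a nominal 5% test is 2·P(T > c × ratio), with T on n − p degrees of freedom and c the critical value. With t on 28 df, c = 2.048 and c × ratio = 1.979, giving 5.8%. With a normal reference, c = 1.960 and the result is 6.9%. The normal reference gives 6.0% even with the unbiased standard error, so ML adds only about 0.9 of a point there.

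| Analysed | p | ML standard error too small by | Size with t |
|---|---|---|---|
| 30 | 2 | 3.4% | 5.8% |
| 30 | 3 | 5.1% | 6.2% |
| 30 | 4 | 6.9% | 6.7% |
| 24 (assumed) | 2 | 4.3% | 6.0% |
| 20 (assumed) | 2 | 5.1% | 6.2% |

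**2. Visit outcomes.** A general linear model fitted by least squares with residual degrees of freedom already divides by n − p, so its ratio is 1. The shortfall arises only if the ML instruction is applied literally.

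**3. Daily model with a person-level random effect for the baseline-to-treatment change.** The arm-by-phase contrast is then a comparison of 30 person-level changes, and step 1 applies. ML and REML fits to simulated null data (300 runs) gave a median standard-error ratio of 0.966. A larger null simulation (random-intercept SD equal to the residual SD, no missing days) gave these sizes for t on 28 df:

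| SD of change / daily residual SD (assumed) | Runs | ML | REML | Zero-variance fits |
|---|---|---|---|---|
| 0.25 | 8,000 | 4.8% | 4.3% | 33.5% |
| 0.5 | 40,000 | 5.9% | 5.1% | 2.8% |
| 0.75 | 40,000 | 5.6% | 4.9% | 0.1% |

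At 0.25 there is no inflation with t.

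**4. Daily model with a random intercept only.** The contrast is judged against within-person residuals. With 30 people and 21 days there are 30 × 20 = 600 within-person comparisons, two of them used by the phase and arm-by-phase terms. The ML ratio is √(598/600) = 0.998, about 0.2% too small. The between-person arm term still shows 0.967.

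This model has another problem if people truly differ in their change. With residual variance 1 and SD of change τ, the true variance of one person's change is 1/7 + 1/14 + τ² = 0.214 + τ². The model uses 0.214 times a residual variance of about 1 + (28 × 4.667/598)τ², where 4.667 = 7 × 14/21. For τ = 0.25, 0.5 and 0.75 the standard-error ratios are 0.886, 0.698 and 0.557. Simulated type I error with a normal reference was 8.0%, 17.4% and 27.4%. These figures come from leaving out the random change effect. REML would not repair them.

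**The case against.** The strongest reply has four parts.

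- **The daily claim is conditional.** A reader might infer that every daily craving and pain contrast has a standard error about 3.5% too small. The documents do not support that. They say only that multilevel modelling will be used, and with a random intercept alone the ML effect on the contrast is about 0.2%. This stands.
- **The large error rates are not caused by ML.** A reader might attribute the 8% to 27% figures to the estimator. They follow from a model that the plan neither sets nor excludes, under assumed SDs. This stands. What remains is that the random effects need to be stated.
- **ML may be loose wording.** The visit outcomes are assigned a general linear model, which is commonly fitted by least squares and would then have no shortfall. Opioid use has no stated scale, and if it is a count or a yes/no outcome the n against n − p formula does not apply. Both stand, so the point is confined to a literal reading and to continuous outcomes.
- **The consequence is small.** With 28 degrees of freedom, a 95% interval for a variance already runs from 0.63 to 1.83 times its estimate. A bias of 1 − 28/30 = 6.7% in the variance is minor beside that. A reader might also infer that a later trial will be undersized, but the plan does not say that this pilot's variance will be used to size one.

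None of this removes the basic fact that ML is written as the method for all these models, with no small-sample provision, in at most 30 people.

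**Conclusion.** The concern holds as a minor point. With 30 analysed and two arm means, literal ML makes the standard error 3.4% too small, and a nominal 5% test runs at about 5.8% with t. Added covariates or dropout increase this; with 20 analysed and two arm means the shortfall is 5.1%.

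The result rests on three conditions: ML is applied as written, the outcome is continuous, and the tested contrast is a person-level one. For the daily models the last condition means a random effect on the change (or slope), or a between-person term. The alpha of 0.05 and the reduced sample sizes are assumptions.

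The unstated random effects can matter more than the estimator, but that is an omission and not an error in what the plan says. Nothing in the documents shows that a random-intercept-only model is intended.

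**What to change.** In the SAP paragraph on Aims 2-3 and the exploratory aims:

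1. For daily multilevel models of continuous outcomes, replace maximum likelihood with REML, and name Satterthwaite or Kenward-Roger degrees of freedom.
2. State person-level random effects for the intercept and for the baseline-to-treatment change, or for the day slope if that is what is tested.
3. State a fallback for non-convergence: each person's treatment-day mean minus baseline-day mean, compared between arms on n − 2 degrees of freedom.
4. Say that the visit general linear models are fitted with residual degrees of freedom.

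The cost is wording only, with no new data. Intervals widen by about 3.5% for a two-arm contrast with 30 analysed. Compared with a random-intercept-only model they widen further when people differ in their change, which is the honest width. The change variance will sometimes be estimated at zero: in about a third of simulated runs when its SD was 0.25 of the residual SD, and in under 3% at 0.5 or above.
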